## 6.5. Treatment Phase

All subjects enrolled in the trial will be treated for 24 weeks across six 28-day treatment cycles.

In total, 9 doses of MOR202 will be administered on the following treatment days: Cycle 1 Day 1, 8, 15 and 22, and on Day 1 of Cycle 2 to 6 (for details see [Figure 1](#) and [Table 2](#)).

The Treatment Phase ends with the EOT visit, scheduled between 28 and 42 days after the last administration of MOR202. For details see [Section 10.4](#).

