### **8.8.4. Withdrawal due to Subject Decision**

Each subject is free to withdraw from the clinical trial at any time. All efforts will be made to complete and report the observations up to the time of withdrawal as thoroughly as possible. A complete final evaluation at the time of the subject's withdrawal should be made (all assessments scheduled for EOT/EOS visit depending on time of withdrawal). An explanation why the subject

is withdrawing from the clinical trial should be provided. If withdrawn in the treatment phase, these subjects will not enter the follow-up phase.

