#### **8.8.5. Withdrawal due to Use of Prohibited Therapy [Immunosuppressive Therapy]**

Subjects starting on prohibited IST other than MOR202 will be withdrawn from the clinical trial. If withdrawn in the treatment phase, these subjects will immediately be scheduled for their EOT visit (at least 28 days after the last MOR202 dose) and will not enter the follow-up phase.

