### Proteinuria Response

Proteinuria responses are reflected by the reduction of proteinuria as measured by UPCR. Based on the proteinuria responses, the following response categories are defined by this clinical trial:

- Proteinuria Complete Response (Prot-CR): Reduction of proteinuria to less than 0.5 g/g, serum albumin within the reference range (3.5 – 5.2 g/dL) and stable eGFR (at least 80% of baseline)
- Proteinuria Partial Response (Prot-PR): Reduction by at least 50% of UPCR at a given visit compared to baseline, proteinuria below 3.0 g/g and stable eGFR (at least 80% of baseline), but not meeting Prot-CR

The following variables related to proteinuria responses are defined as follows.

Overall Proteinuria Response (OPR), defined as subjects achieving either Prot-CR or Prot-PR as a response (irrespective of start of prohibited medication or progressive disease prior to the proteinuria response).

Time to First Proteinuria Response (in months) prior to start of prohibited treatment or progression, defined as

[Date of first documented response of Prot-CR or Prot-PR (whichever is earlier) – Start of study drug + 1 day]/30.4375

Best Proteinuria Response (BPR) for a subject is defined when a subject is classified as having a Prot-CR or Prot-PR at any time during the trial but prior to start of prohibited treatment or progression. Responses for BPR are ordered as Prot-PR < Prot-CR. If a subject meets the criteria for more than one response category, the subject will be classified in the highest category.

Time to BPR (in months), defined as

[Date of BPR – Start date of study drug + 1 day]/30.4375

Duration of Proteinuria Response, defined as

[Date of death, PD or start of prohibited treatment (whichever is earlier) – Date of first documented response of Prot-CR or Prot-PR (whichever is earlier) + 1 day]/30.4375. Subjects with a response but no date of death, PD or start of prohibited treatment at the time of analysis

cut-off will be censored at the date of last response assessment. Subjects without a response of Prot-CR or Prot-PR are assigned a duration time of zero.

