### 10.1. Analysis of best immunological response rate

The key secondary objective in this trial is to assess the effect of MOR202 on serum anti-PLA2R antibodies in subjects with aMN in terms of best overall immunological response rate (BIRR).

The best overall immunological response (BIR) is defined as achieving any response of IPR, ICR or sICR at any time during the trial but prior to start of prohibited medication or progression based on the definitions in section 7.13.3.

The best overall immunological response rate (BIRR) is defined as the proportion of subjects with a best overall immunological response. The denominator will be the total number of subjects included in the analysis population.

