#### Main Analysis

The main analysis will be conducted on FAS. The following information will be presented by cohort and overall:

- Number (%) of subjects achieving a BIR of IPR at any time during the trial
- Number (%) of subjects achieving a BIR of ICR at any time during the trial
- Number (%) of subjects achieving a BIR of sICR at any time during the trial
- BIRR along with the 95% confidence interval (CI, using the Clopper-Pearson exact method)
- Number (%) of subjects with a BIR of PD at any time during the trial
- Number (%) of subjects classified as Non-responder

For each visit available, the number and percentages of subjects in each of the response categories will be tabulated, including missing response evaluations and subjects with a progressive disease. Subjects, who are not classified in either response category or progressive disease will be tabulated as “*Non-Responders*”. Subjects with no post-baseline assessment of response will be included as “*Non-Responders*”.

If a subject achieves several responses, the subject will be tabulated in the highest achieved response category.

No formal hypothesis testing will be conducted.

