## 10.2. Analysis of 24 hour urine

24 hour urine will be collected to assess the following parameters:

- Urine protein
- Urine creatinine
- Urine sodium
- CCI [REDACTED]

The following information will be summarized for each 24 hour urine parameter above by cohort and overall on FAS:

Absolute levels by visit

Absolute and percentage change from baseline to each visit until end of study

Listings with individual urine parameter levels will be generated by visit on FAS.

- The following plots will be generated by cohort on FAS for UPCR and Urine creatinine:
  - Spaghetti plots (time vs. parameter value for each subject)
  - Spaghetti plots (time starting from baseline vs. % change from baseline for each subject) – please add dotted reference lines for upper (50%) and lower (-50%) thresholds.
  - Waterfall plot for relative change from baseline at EOT, FUV and EOS – please add study days under the corresponding subject IDs

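### The by-visit response table and the 24-hour urine outputs have no cut-off for values taken after rescue immunosuppression, although best immunological response has one

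*Protocol*

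**What the plan says.** **Timing of the visit.** Protocol 8.8.5: "Subjects starting on prohibited IST other than MOR202 will be withdrawn from the clinical trial". If this happens in the treatment phase, "these subjects will immediately be scheduled for their EOT visit (at least 28 days after the last MOR202 dose", and there is no follow-up phase. Protocol 6.5 gives the usual EOT window: "scheduled between 28 and 42 days after the last administration of MOR202". Table 2 schedules both anti-PLA2R and a 24-hour urine collection at EOT.

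**Rule for the headline variable.** SAP 10.1 counts a BIR "at any time during the trial but prior to start of prohibited medication or progression". SAP 7.13.3 and the censoring table in 7.13.5 apply a cut-off at prohibited treatment to best proteinuria response (BPR) and to the time-to-response variables as well.

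**Rule for the by-visit outputs.** The same SAP section continues: "For each visit available, the number and percentages of subjects in each of the response categories will be tabulated". That table has places for missing evaluations, progressive disease and non-response, but none for prohibited therapy. SAP 10.2 asks for absolute values and changes from baseline at every visit on the full analysis set (FAS), and for a "Waterfall plot for relative change from baseline at EOT, FUV and EOS". No prohibited-therapy limit is stated there.

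**The concern.** This is a single-arm trial, so a fall in titre or in the urine protein-to-creatinine ratio (UPCR) at EOT will be read as an effect of MOR202. Protocol 8.4 includes plasmapheresis and immuno-adsorption among the prohibited therapies, and the Amendment 5 summary says they were added because they affect outcome parameters. The SAP document history (version 3.0) gives the matching reason for the BIR cut-off: assessments after prohibited treatment or progression should not feed the derivation of responses.

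The by-visit table displays the key secondary variable, and its response categories are laboratory criteria alone (titre, plus immunofluorescence for the stringent category). A subject with no response before rescue, whose titre then falls under rescue, would be a non-responder in BIRR and could be an IPR or ICR at EOT in the table beside it. The 24-hour urine means and waterfall plot would likewise mix values under MOR202 with values under another drug, without marking which are which.

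**Working it through.** The plan gives no figure on this point. Its only related numbers are the cohort sizes in Protocol 12.5. The detection probabilities stated there reproduce (1 − 0.90^20 = 0.878 against 88%; 1 − 0.85^10 = 0.803 against 80%) and are not in dispute.

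**1. When is the EOT sample taken relative to rescue?** Let s be the number of days from the last MOR202 dose to the start of IST. The documents do not give s, so it is varied. With EOT on day 28 to 42 after the last dose, days since rescue began = (28 − s) to (42 − s) for s up to 28:

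| s | Days since rescue began, at EOT |
|---|---|
| 1 | 27 to 41 |
| 7 | 21 to 35 |
| 14 | 14 to 28 |
| 21 | 7 to 21 |
| 27 | 1 to 15 |
| 28 | 0 to 14 |

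Any IST start before day 28 puts the whole EOT window after the start of rescue.

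**2. Would such a value be tabulated?**
- SAP 7.10 uses the nominal eCRF visit, so an early EOT is still EOT.
- SAP 8.4 includes data up to the cut-off date, and Protocol 12.6 includes all data from dosed subjects where appropriate.
- The exclusion in SAP 7.12.8 and 8.4 concerns withdrawal of consent. Withdrawal for IST is not withdrawal of consent.

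Inclusion is therefore the default, although the SAP does not say so in words.

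**3. Which planned analyses remove it?**
- SAP 10.1 repeats the main analysis on the per-protocol set (PPS). This helps if IST use is listed as an excluding deviation; the form that decides this is not part of the documents.
- SAP 10.10 drops subjects who received relevant IST. Its legible endpoints are BIRR, eGFR, serum albumin and anti-PLA2R kinetics. One entry is redacted, and section 10.2 is not legibly listed.
- SAP Table 7-1 plans the 24-hour urine summary on FAS only.

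**4. Weight of one subject.** At the planned sizes, one subject is 1/20 = 5 points in Cohort 1, 1/10 = 10 points in Cohort 2 and 1/30 = 3.3 points overall.

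**5. Illustration (assumed counts, Cohort 2).**
- Post-rescue response counted: 6/10 = 60% (Clopper-Pearson 95% CI 26.2 to 87.8).
- Subject kept in the denominator but not counted as a responder: 5/10 = 50% (18.7 to 81.3).
- Subject removed altogether, as in 10.10: 5/9 = 55.6%. The treatment failure disappears with the post-rescue value, which answers a different question.

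**6. Urine means.** If rescue shifts one subject's percentage change in UPCR by an assumed 50 points, the mean moves by 50/10 = 5.0, 50/20 = 2.5 or 50/30 = 1.7 points. After baseline, 24-hour urine is scheduled only at C4D1, EOT, FUV and EOS. For a subject withdrawn for IST before C4D1, EOT is therefore the only scheduled post-baseline 24-hour value.

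**The case against.** The other side has a good deal of force. BIRR, BPR and the time-to-response variables are all protected. What is left is descriptive, in a trial without hypothesis tests, and a table of observed values by visit is a legitimate summary of a different kind from BIR. The PPS repeat and 10.10 each give a view of section 10.1 without these subjects. Individual responses and urine values are listed, and the waterfall plot prints study days, so an early EOT can be traced. Anti-PLA2R is drawn before every dose, so a recent titre from before rescue normally exists. All of this stands, and it limits the point to a display rule. It does not supply that rule: a reader of the FAS by-visit table cannot see which EOT responses came after rescue.

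Four stronger readings are tempting and are not supported:

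- *That Protocol 8.8.5 contradicts itself or 8.8.4.* The booking is immediate and the visit falls on day 28 or later, in line with 8.8.1 and 8.8.2. Section 8.8.4 ("all assessments scheduled for EOT/EOS visit depending on time of withdrawal") concerns subjects who leave by their own decision, and different timing there is not a contradiction.
- *That EOT is usually under rescue.* This depends on s, which is not given. A subject who stops MOR202 and starts IST only after EOT is unaffected, as is one who starts IST during follow-up.
- *That EOT response is overstated by up to 10 points overall (3/30).* This treats every one of the roughly 10% expected discontinuations as a rescue case and assumes that all of them respond to rescue. The 10% covers any cause.
- *That overall proteinuria response is defective.* SAP 7.13.3 says it is counted "irrespective of start of prohibited medication or progressive disease prior to the proteinuria response" and pairs it with BPR, which is cut off at prohibited treatment. The pair is explicit. The section that tabulates proteinuria response is redacted, so its by-visit handling cannot be judged.

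**Conclusion.** The point holds as a gap in the SAP's display rules. For a subject who starts prohibited IST in the treatment phase and before the EOT visit, the EOT titre and 24-hour urine values follow the start of rescue. The by-visit table in SAP 10.1 and the outputs in SAP 10.2 would show them unmarked. The 10.1 table is partly covered by analyses that remove whole subjects; the 10.2 outputs have no legible cover.

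The size is at most 5, 10 and 3.3 percentage points per such subject in Cohort 1, Cohort 2 and overall. This assumes the planned 20 and 10 subjects as denominators and a subject who meets a response category at EOT only after rescue. The number of such subjects is not given, so no total is claimed. The headline immunological response rate is not affected.

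**What to change.** Change the SAP only:

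- **Section 10.1, by-visit table.** Place assessments on or after the first prohibited-medication date (SAP 7.13.6) in a separate 'after prohibited therapy' row. Keep these subjects in the denominator and do not count them as IPR, ICR or sICR.
- **Section 10.2.** Flag these values in the waterfall and spaghetti plots. Present the change-from-baseline summaries with and without them.

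The date is already needed for BIR, BPR and the time-to-response variables, so nothing new has to be collected or derived. The cost is one extra row or column per table and slightly fewer values in the 'without' summary. Where only the month of the prohibited medication is known, 7.13.6 sets the date to the first of that month, so an assessment earlier in the month than the true start would also fall in the new row; a footnote can say so.

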### **8.9. Subject replacement**

After safety run-in, withdrawn or discontinued subjects will not be replaced.

### **8.10. IMP Accountability**

The assigned pharmacist or other designated individual at the site will maintain up-to-date records:

- Of IMP delivered to the site
- The dispensation to and use by each subject
- And the return of unused IMP to the sponsor or disposal

## **9. TRIAL PAUSING OR TERMINATION**

### **9.1. Safety Review Triggers and Decision Making**

After completion of the safety run-in, toxicities leading to discontinuation will be continuously monitored. Recruitment into the MOR202C103 clinical trial will be paused in the following situation until a safety review by the Safety Review Panel consisting of representatives of the participating investigators and the sponsor (as defined in [Section 6.3](#)) is performed:

- If at any time treatment with MOR202 had to be discontinued due to the reasons listed in [Section 8.8.1](#) in at least 2 subjects treated.

The safety review will consist of an evaluation based on the number and type of AEs and laboratory values (biochemistry and hematology) and will be performed by representatives of the participating investigators and the sponsor as defined in a respective charter. Based on the assessment, the Safety Review Panel (see [Section 6.3](#)) will decide on further steps, e.g. pause of dosing in all subjects, introduction of any required protocol changes or trial termination due to unacceptable toxicity.

Additional safety review may be triggered at any time if any of the following occur:

- Thrombocytopenia  $\geq$  grade 3 in at least 4 subjects
- IRR  $\geq$  grade 3 in at least 4 subjects
- A single patient is not recovering to  $\leq$  grade 2 from  $\geq$  grade 3 ADRs related to MOR202 within 21 days despite adequate treatment of the ADR.

The Safety Review Panel will convene, perform a safety review and make recommendations as outlined above.

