## 6.8. Risks and Benefits to Subjects

CCI

Similar safety findings were also observed in the FiH trial MOR202C101 (see [Section 4.2](#) and [Section 6.1.2](#)). In this trial administering MOR202 to MM subjects the most frequent MOR202 related treatment emergent adverse events (TEAEs) were thrombocytopenia, neutropenia, lymphopenia, and infections. No ADAs were detected in this trial until the primary completion date (samples analyzed from 85 subjects treated for up to 29 months at a maximum) ([Jarutat 2018](#)).

It is expected that the potential risks as described above will be adequately controlled by the design of this trial (e.g. by the inclusion and exclusion criteria) as well as by frequent monitoring for potential ADRs. Since a major pharmacological effect of MOR202 is depletion of plasma cells and plasmablasts, the risk for a potentially reduced function of the adaptive immune system was further addressed. This comprises monitoring and potential substitution of total serum immunoglobulin as well as vaccination before trial start (see Section 7.1 and Section 7.2).

MOR202 offers a novel mechanism of action that may have the potential to emerge as an important treatment option for aMN patients compared to current (off-label) treatment options. Particularly with calcineurin inhibitors (CNIs) being intrinsically nephrotoxic and cyclophosphamide as an alkylating cytotoxic drug being associated with known hematotoxicity, risk of ovarian insufficiency and secondary malignancy, new therapeutic options are needed for the treatment of MN. Recent literature suggests that RTX, although more favorable in the safety profile compared to the aforementioned drugs, might have decreased activity in high antiPLA2R antibody titer subjects (Ruggenti et al 2015). This patient population is specifically addressed by Cohort 1 of this trial.

Non response to an immunosuppressive regimen may be caused by survival of long-lived plasma cells producing anti-PLA2R antibodies. These cells demonstrate a high expression of MOR202's target CD38. This patient population is specifically addressed by Cohort 2 of this trial.

In this context and taking into account the existing clinical experience with MOR202, the overall risk/benefit ratio for the trial subjects is regarded as acceptable.

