### 8.7. Treatment management of subjects with toxicity

For the first dosing of MOR202, subjects should exhibit hemoglobin, leucocyte, neutrophil and platelet counts meeting the eligibility criteria. They should not have an active infection  $\geq$  grade 2.

For subsequent doses, in case a subject shows laboratory values as listed below, further treatment of the subject has to be interrupted:

- Hemoglobin level < 60 g/L (grade 3): interruption until resolved to  $\geq 80$  g/L.
- Platelet count <  $75.0 \times 10^9/L$  (grade 2): interruption until resolved to  $\geq 100.0 \times 10^9/L$ .
- Neutrophil count <  $1.000 \times 10^9/L$  (grade 3): interruption until resolved to  $\geq 1.500 \times 10^9/L$ .

If the subject exhibits any other clinically relevant adverse drug reaction  $\geq$  grade 3, MOR202 administration has to be interrupted until the toxicity has resolved to grade 2 or better.

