## **8.8. Subject Discontinuation of IMP and Subject Withdrawal**

### **8.8.1. Discontinuation due to toxicity**

MOR202 treatment must be permanently discontinued, if:

- Needing platelet transfusion.
- Not recovering to  $\leq$  grade 2 from  $\geq$  grade 3 ADRs related to MOR202 within 21 days despite adequate treatment of the ADR.
- Experiencing grade 4 IRR.

Subjects discontinuing MOR202 treatment will have their EOT visit (earliest after 28 days after last dose of MOR202) and enter the follow-up phase.

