### 10.8.7. Adverse Events of Special Interest (AESI)

AEs of special interest (AESI) in this clinical trial should be reported along with their respective symptoms (e.g. hives, chills, and fever for infusion reaction) using the trial specific SAE report form.

AESIs include:

- Infusion related reactions to MOR202  $\geq$  grade 3
- Cytokine release syndrome
- Allergic reactions to MOR202
- Infections  $\geq$  grade 3
- Neutropenia  $\geq$  grade 3 ( $< 1.0 \times 10^9/L$ )
- Thrombocytopenia  $\geq$  grade 3 ( $< 50.0 \times 10^9/L$ )
- Major bleeds (defined as critical organ bleed or hemoglobin decrease of more than 20 g/L within 24 h)

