### 10.8.9. Assessment of AEs, SAEs and AESIs

As far as possible, each AE should be evaluated to determine the following:

- Relationship to trial drug (suspected/not suspected).
- Duration (start and end date or if continuing at EOS).
- Intensity: The intensity of all AEs will be graded as mild, moderate, or severe using the following definitions:
  - o **Mild:** Tolerable
  - o **Moderate:** Interferes with normal activity
  - o **Severe:** Incapacitating (causes inability to perform usual activity or work).
- Toxicity grade (severity): The toxicity grade of AEs will be graded according to the NCI-CTCAE version 5.0 of November 27, 2017 using the following definitions:
  - o Grade 1: Mild; asymptomatic or mild symptoms; clinical or diagnostic observations only; intervention not indicated.
  - o Grade 2: Moderate; minimal, local or non-invasive intervention indicated; limiting age-appropriate instrumental activities of daily living (refers to preparing meals, shopping for groceries or clothes, using the telephone, managing money, etc.)
  - o Grade 3: Severe or medically significant but not immediately life-threatening; hospitalization or prolongation of hospitalization indicated; disabling; limiting self-care activities of daily living.
  - o Grade 4: Life-threatening consequences; urgent intervention indicated.
  - o Grade 5: Death related to AE.
- Seriousness
- Outcome

- Action taken (no action taken; trial drug temporarily interrupted; trial drug permanently discontinued due to this AE; concomitant medication taken; non-drug therapy given; hospitalization/prolonged hospitalization)).

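### After the run-in, Protocol 9.1 lists no Safety Review Panel trigger for repeated related grade 4 infection or neutropenia that recovers within 21 days

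*Protocol*

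**What the plan says.** After the run-in, Protocol 9.1 gives two kinds of trigger.

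- **Recruitment pause with review.** "If at any time treatment with MOR202 had to be discontinued due to the reasons listed in" Section 8.8.1, in at least two subjects. The 8.8.1 reasons are platelet transfusion, a grade 4 infusion-related reaction (IRR), and failure to recover to grade 2 or lower from at least "grade 3 ADRs related to MOR202 within 21 days despite adequate treatment of the ADR".
- **Additional review.** "Additional safety review may be triggered at any time if any of the following occur": thrombocytopenia of grade 3 or higher in at least four subjects; IRR of grade 3 or higher in at least four subjects; or a single patient with a related grade 3 or higher reaction not recovered within 21 days. The section then states: "The Safety Review Panel will convene, perform a safety review and make recommendations as outlined above".

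For the individual subject, Protocol 8.7 holds dosing when neutrophils fall below 1.0 × 10⁹/L and allows it again only at 1.5 × 10⁹/L or above. For any other clinically relevant drug reaction of at least "grade 3, MOR202 administration has to be interrupted until the toxicity has resolved to grade 2 or better".

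On expected risk, Protocol 6.8 reports that in the earlier myeloma trial "the most frequent MOR202 related treatment emergent adverse events (TEAEs) were thrombocytopenia, neutropenia, lymphopenia, and infections". Protocol 10.8.7 makes infection and neutropenia events of special interest from grade 3. Protocol 10.8.9 defines the top non-fatal grade as "Grade 4: Life-threatening consequences; urgent intervention indicated". SAP 6.4.1 describes only the run-in review and adds no later trigger.

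**The concern.** Of the four event types that 6.8 singles out, only thrombocytopenia has its own count across subjects in 9.1. Infection and neutropenia reach the panel only if an event persists beyond 21 days or the same subject meets a different trigger. The 21-day rule detects persistence. It does not detect the same serious event recurring in one subject after another.

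Safety is the primary objective, and the panel is the body the protocol names for review across subjects. If 9.1 is followed as written, several related grade 4 infections or neutropenias could each be treated, recover and be followed by renewed dosing, with no listed requirement that the panel look at them together. Investigator decisions to stop treatment do not close the gap: stops under 8.8.2 do not count toward the pause, because 9.1 refers only to 8.8.1.

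**Working it through.** **1. The plan's own figure.** Section 9.1 gives no operating characteristics. The nearest figures are in Protocol 12.5, the chance of seeing at least one occurrence of an adverse event, 1 − (1 − p)ⁿ:

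- Cohort 1: 1 − 0.90²⁰ = 0.878 (stated 88%).
- Cohort 2: 1 − 0.85¹⁰ = 0.803 (stated 80%).

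Both reproduce. They concern observing one event, not triggering a review.

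**2. Each route in 9.1 against the case in question** (related grade 4 infection or neutropenia, back to grade 2 or lower within 21 days, no platelet transfusion):

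| Route | Met? |
|---|---|
| Two or more 8.8.1 discontinuations | No: none of the three 8.8.1 reasons applies |
| Thrombocytopenia grade ≥3 in ≥4 subjects | No: different event |
| IRR grade ≥3 in ≥4 subjects | No: different event |
| One related grade ≥3 reaction unrecovered at 21 days | No: it recovered |

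The answer is the same for one affected subject or for 27.

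**3. Chance of at least two affected subjects.** About 20 + 10 = 30 subjects are planned (12.5), so 27 follow the three run-in subjects. The per-subject probability p of a related grade 4 infection or neutropenia (combined) is an assumption, with subjects taken as independent.

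P(≥2) = 1 − (1 − p)²⁷ − 27p(1 − p)²⁶

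- p = 1%: 1 − 0.7623 − 0.2079 = 0.030
- p = 2%: 1 − 0.5796 − 0.3194 = 0.101
- p = 5%: 1 − 0.2503 − 0.3558 = 0.394
- p = 10%: 1 − 0.0581 − 0.1744 = 0.767

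With all 30 subjects, since run-in subjects also come under 9.1 later, the same formula gives 4%, 12%, 45% and 82%.

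**4. From affected subjects to the gap.** Step 3 counts every related grade 4 event. A single one that does not recover in 21 days already meets a listed trigger, so step 3 is an upper bound. To illustrate, assume 70% recover in time. The gap is then two or more recovered events and no unrecovered one:

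P(gap) = (1 − 0.3p)²⁷ − (1 − p)²⁷ − 27(0.7p)(1 − p)²⁶

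- p = 1%: 0.9221 − 0.7623 − 0.1455 = 0.014
- p = 2%: 0.8500 − 0.5796 − 0.2235 = 0.047
- p = 5%: 0.6649 − 0.2503 − 0.2490 = 0.166
- p = 10%: 0.4394 − 0.0581 − 0.1221 = 0.259

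At p = 5% the gap is about 17%, against the 39% of step 3. A higher recovery share moves it toward the upper bound, a lower one away from it.

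**The case against.** The other side has substance.

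- **Deliberate design.** Section 9.1 is built around toxicity that leads to discontinuation, and Amendment 2 records that its triggers were tightened at a regulator's request. The panel works under a charter that is not available and may list more. This stands, and it limits the point to what 9.1 itself lists.
- **A backstop exists.** One related grade 3 or higher reaction of any type that fails to recover in 21 days is a listed trigger. This stands, and it is why the figures in step 3 are only an upper bound.
- **The risk evidence is indirect.** The 6.8 statement carries no grades. It comes from a trial in which MOR202 was given alone or in combinations, and Protocol 4.2.2 calls the combination drugs intrinsically myelosuppressive and the cytopenias manageable. The present trial is monotherapy. A reader might infer that frequent grade 4 events are expected here; the documents do not support that.
- **Subject-level safeguards.** These are the 8.7 neutrophil rule, a local blood count within 48 hours before each dose (10.4), immunoglobulin monitoring (8.3.2), 24-hour reporting of events of special interest (10.8.10) and investigator discretion (8.8.2). They make the gap smaller. They act subject by subject or at someone's discretion, and none requires the panel to look across subjects.
- **The count of two is not derived.** Correct; it is a judgement.

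Two stronger readings are tempting. One is that 9.1 contradicts the run-in rule in 6.3, where any single grade 4 or 5 related reaction forces a review. It does not: a stricter gate for the first three subjects is an ordinary choice. The other is that a related death would escape review. On an ordinary reading, a fatal event is one that has not recovered, so the single-patient trigger covers it.

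**Conclusion.** The gap is real and narrow. After the run-in, no trigger listed in 9.1 is met by related grade 4 infection or neutropenia that recovers within 21 days, at any number of subjects, although the protocol treats both as events of special interest from grade 3. That conclusion rests on the text alone and would change only if the charter contains a further trigger.

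Its size cannot be fixed from the documents, which give no rate in this population. With 27 later subjects, the chance of two or more affected is at most 3%, 10%, 39% and 77% at assumed rates of 1%, 2%, 5% and 10%. If 70% of events recover in time, the chance that two or more pass with no listed trigger met is about 1%, 5%, 17% and 26%. A reader might take 39% or 77% as the chance that repeated events go unreviewed; that would hold only if essentially all of them recovered in time.

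There is also a small wording mismatch: the additional review is introduced with *may*, while the closing sentence says the panel *will* convene. The point is a cheap improvement to the safety plan. It does not show that the trial was unsafe.

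**What to change.** In the additional-review list of Protocol 9.1:

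1. Add: *related grade 4 infection or related grade 4 neutropenia in at least 2 subjects*, leading to a panel review without an automatic recruitment pause. The sponsor may set a different count. Two is 2/30 = 6.7% of planned subjects, against 4/30 = 13.3% for the existing thrombocytopenia and IRR counts; the lower count reflects the higher grade.
2. Change *may* to *will* in the lead-in, so that it agrees with the closing sentence.
3. Mirror both in the panel charter. If the charter already has such a trigger, bring it into 9.1.

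No separate line for fatal events is needed. Sections 6.3, 8.7 and 8.8.1, the existing counts and the pause rule stay as they are.

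**Cost.** The panel exists and the events already arrive within 24 hours, so the running cost is a few extra meetings at most. The new trigger would be met with probability of about 10% at an assumed 2% rate, 39% at 5% and 77% at 10% (12%, 45% and 82% if all 30 subjects count). The text has to go through a protocol amendment, with ethics and authority approval as required, at about 55 planned sites, so it is best carried with another amendment. The benefit applies only while subjects are still being dosed.
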